3.7 Treatment assignment and treatment groups

It is expected that subjects receive treatment as randomized and hence safety analyses will be based on the SS, as randomized. However, if after unblinding it is determined that subjects randomized to placebo received bimekizumab at any time, then for safety analyses these subjects will be reallocated to the appropriate bimekizumab treatment group. Subjects randomized to bimekizumab will only be reallocated to the placebo treatment group if they did not receive bimekizumab at any time during the study.

Depending on the analysis sets, subjects will be summarized and listed based on the actual received treatment or according to the randomization which will be considered as planned treatment:

- All subjects screened/ES: planned treatment
- RS: planned treatment
- SS: actual treatment
- FAS: planned treatment
- PPS: planned treatment
- PK-PPS: actual treatment
- PD-PPS: actual treatment
- DBS: planned treatment (demographics, baseline characteristics, and efficacy analyses) or actual treatment
- ESS: planned treatment
- DBRS: planned treatment
- cESS: planned treatment
- cDBRS: planned treatment

3.8 Center pooling strategy

Centers will be pooled into geographic regions for analysis purposes. Centers will be grouped in the geographic regions North America and Europe.

3.9 Coding dictionaries

Medical history and AEs will be coded using the Medical Dictionary for Regulatory Activities (MedDRA) version 19.0. Previous and ongoing medical history will be classified by primary system organ class (SOC) and preferred term (PT).

All AEs will be classified by primary SOC, high level term and PT. Prior and concomitant medications will be coded using version SEP2015 of the World Health Organization Drug Dictionary (WHO-DD) and will be classified by Anatomical Main Group, Pharmacological Subgroup, and PT. Medical procedures will not be coded.

3.10 Changes to protocol-defined analyses

The PK variables total body clearance (CL/F) and volume of distribution (V/F) will be analyzed separately. CL/F and V/F variables were removed from the PK variable list.

Following two subgroup analyses were added: time since first diagnosis of PsA and body weight.

Instead of stopping the pairwise testing of each bimekizumab dose versus placebo once it failed to reach significance at a significance level of $\alpha=0.05$, the pairwise testing will continue and further pairwise comparisons are seen as non-significant.

No fixed sequence testing will be used for the secondary efficacy variables.

The other efficacy variable modified MDA was added to the analysis. The definition for the modified MDS is available in [Section 8.3.1](#).

Time to a given response is defined as the length in weeks from Baseline until the first date when the response is achieved. In the definition the length was changed from days to weeks due to easier interpretation.

Two addition analyses were added in the section analysis of other efficacy variables. A frequencies table counting the number of subjects with $\text{PSAID-9} \leq 3$ as well as cumulative distribution function (CDF) plots of PSAID-9 change from Baseline to Week 12 and Week 12 to Week 48 by treatment group.

4 STATISTICAL/ANALYTICAL ISSUES

4.1 Adjustments for covariates

The primary efficacy analysis and secondary analysis will be adjusted for treatment, geographic region, and prior TNF inhibitor exposure (yes/no).

4.2 Handling of dropouts or missing data

4.2.1 Handling of missing data for efficacy analysis

The analysis for the binary primary, secondary, and other efficacy variables will use non-responder imputation (NRI) for handling missing data. In NRI, each subject with missing data or who has discontinued Double-Blind study treatment prior to Week 12 will be counted as a non-responder.

Sensitivity analysis will be performed for the secondary analysis of the primary variable (ACR50 response at Week 12) using MI assuming that missingness is missing at random (MAR). The MI method will be applied as follows:

1. Create a data set, sorted by treatment groups, of subjects with observed values and those needing estimation by multiple imputation. For the imputation step, missing values will be separated into non-monotone missing values (ie, intermittent missing values between completed assessments) and monotone missing values (ie, missing values after the patient dropped out). The procedure will sequentially estimate an imputation model for the ACR components at each post-Baseline visit where ACR components are collected, with geographic region, and prior TNF inhibitor exposure as covariates separated between the treatment groups.

- For the imputation of intermediate missing values, the missing ACR components in each data set will be filled in using the Markov-Chain Monte Carlo (MCMC) method with multiple chains and monotone imputing. A total number of imputations will be 100. The seed used for these imputations will be 2017.

Note: All other multiple imputation procedures described in this SAP will use this same seed as well.

Note: The imputation model based on the MCMC method will only allow continuous variables as predictors. Therefore, prior TNF inhibitor exposure and geographic region will be re-coded as indicator variables (with values of 0 or 1 for each level of the variable).

Note: To avoid that imputed values are outside of the pre-defined range of values for the ACR components (eg, HAQ-DI [0-3]) maximum and minimum values for imputed variable values are specified.

- If the intermediate missing data are imputed, the monotone missing data will be imputed for all patients with monotone regression including geographic region, and prior TNF inhibitor exposure as covariates. The dataset is the output dataset of the partial imputation. Since this dataset already has 100 imputed values at each visit, only one imputation will be performed.

Note: Maximum and minimum values are specified for imputed variable values to avoid values outside of the pre-defined range of values.

2. The ACR50 response will be calculated using the complete datasets. That is, the values of the ACR components at Week 12 based on the complete datasets will be compared to their corresponding Baseline values to calculate an ACR50 response for each subject (as described in Section 8.1.1). Each complete imputed data set will then be analyzed based on a logistic regression model with factors of treatment group, geographic region, and prior TNF inhibitor exposure as fixed effects.
3. The Week 12 results from the logistic regression analysis of each of the 100 imputed data sets will be combined for overall inference using Rubin's rules, which account for the uncertainty associated with the imputed values (Rubin, 1987).

Some key points to consider relative to the calculation of the odds ratios and corresponding confidence intervals (CIs) are noted below:

As the estimates of the odds ratios from the logistic regression model in step 3 follow a lognormal distribution, a log transformation is needed to normalize these estimates since the procedures for combining results from multiple imputed datasets are based on the assumption that the statistics estimated from each imputed dataset are normally distributed. Therefore, the log of the odds ratio estimates from the logistic regression model are used when combining into a single inference (step 3). Additionally, the standard errors (SE) for the odds ratios are transformed as follows:

$$SE = \frac{\log(UCL) - \log(LCL)}{2Z_{\alpha/2}} \quad (1)$$

where UCL and LCL are the upper and lower confidence limit, respectively, for the CI of the odds ratio from the logistic regression model, and $Z_{\alpha/2}$ is the relevant critical value from the standard normal distribution (1.96 for a 95% CI). The estimates of the log odds ratio for each bimekizumab dose relative to placebo and the corresponding upper and lower confidence limits will be provided. The odds ratio is estimated by exponentiating the estimate of the log odds ratio. The confidence limits of the odds ratio are then estimated as follows:

$$LCL = OR * \exp(-SE * Z_{\alpha/2}) \quad (2)$$

$$UCL = OR * \exp(SE * Z_{\alpha/2}) \quad (3)$$

where OR is the back-transformed estimate of the odds ratio just described, SE is the standard error of the log odds ratio and $Z_{\alpha/2}$ is the relevant critical value from the standard normal distribution (1.96 for a 95% CI). These calculations will be done such that odds ratios and corresponding CIs are calculated for the odds ratio of each bimekizumab dose versus placebo. Note that the p-values presented in the tables are not impacted by the transformations described above.

The supportive analysis number 3 (analysis of the ACR components), and all continuous secondary efficacy variables will use the same MI method as described above. Instead of using the logistic regression model the ANCOVA with treatment group, geographic region, and TNF inhibitor exposure as fixed effects and the Baseline values as covariate will be used. No log transformation is needed for the ANCOVA estimations.

Following Rubin (1987), multiple imputation estimates of descriptive statistics are computed by simply averaging the estimates from $m = 1, \dots, M$ independent repetitions of the imputation algorithm:

$$\bar{\theta} = \frac{1}{M} \sum_{m=1}^M \hat{\theta}_m \quad (4)$$

where $\hat{\theta}_m$ is the estimate of θ from the completed data set $m = 1, \dots, M$ (Berglund, 2014).

The imputation model will be applied for each treatment group separately. However, in the event there are computational challenges with the imputation model (eg, due to a standard deviation of 0 for responses of a given imputation), it is acceptable to modify the imputation model to include treatment as a variable in the model rather than running a separate model for each treatment group. It should be noted that doing so assumes that treatment does not interact with any of the other variables in the imputation model.

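### The multiple imputation model in SAP 4.2.1 does not include the Baseline value, although the ANCOVA of the ACR components adjusts for it and ACR50 is derived from it

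*SAP*

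**What the plan says.** SAP 4.2.1 sets out the MI in detail, under a missing-at-random assumption with 100 imputations. On what is imputed: "The procedure will sequentially estimate an imputation model for the ACR components at each post-Baseline visit where ACR components are collected". On predictors: "with geographic region, and prior TNF inhibitor exposure as covariates separated between the treatment groups". The step for monotone missingness repeats the list: "monotone regression including geographic region, and prior TNF inhibitor exposure as covariates". For the MCMC step the same two factors are recoded as indicators, and no further predictor is named.

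Baseline enters only after imputation, in two places. For ACR50, the Week 12 component values from the completed data "will be compared to their corresponding Baseline values to calculate an ACR50 response for each subject". For supportive analysis 3, "the ANCOVA with treatment group, geographic region, and TNF inhibitor exposure as fixed effects and the Baseline values as covariate will be used".

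On reach, 4.2.1 adds that "all continuous secondary efficacy variables will use the same MI method as described above". The secondary variables in SAP 2.2.1.2 are all binary, so that clause adds nothing by itself. However, SAP 8.3 applies MI to the other continuous variables, and Protocol 15.7 applies it to all continuous efficacy variables. SAP 8.1.5 and Protocol 15.7 describe the imputation as draws conditional on the observed data, without naming Baseline.

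**The concern.** An imputation model should contain every variable that the analysis model uses and every variable from which the endpoint is computed. If Baseline is missing from it, imputed Week 12 values relate to the subject's own Baseline only as far as other observed visits carry that information. This has three consequences:

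- The regression on Baseline is flattened and residual variance inflated, which costs precision.
- The missing-at-random assumption, as implemented, conditions on less than is observed. If dropout depends on Baseline, imputed values are drawn around the wrong mean.
- If that happens equally in all arms, most of the shift cancels in a contrast. If it differs by arm, the contrast is biased.

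At stake are the component contrasts, intervals and p-values of supportive analysis 3, the imputed summaries of the other continuous variables, and one of the three sensitivity analyses of the pairwise ACR50 comparison.

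**Working it through.** **1. Inputs.** From the plan: 40 subjects per arm (SAP 2.4) and the two-item covariate list (SAP 4.2.1). The plan gives no dropout rate, SD or correlation, and no figure for the MI. Its one related figure, power above 99%, reproduces at 99.96% to 99.998% and plays no part here.

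Assumed for one normal component: Baseline mean 60, SD 12; Week 12 mean 50 (placebo-like) or 32 (active-like), SD 16; correlation ρ of Baseline with later visits 0.3 to 0.7; visit-to-visit correlation 0.7; about 10% missing, either completely at random (MCAR) or with the log-odds of dropout rising by 1.0 per Baseline SD. Response means Week 12 at or below half of Baseline.

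**2. Closed-form check (placebo-like, ρ = 0.5, MCAR).** Let D = Y − 0.5B. Its mean is 50 − 30 = 20. Its variance is 16² + 0.25×12² − 2×0.5×r×12×16 = 292 − 192r, where r is the Baseline correlation that the imputed value retains.

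- Truth, r = 0.5: SD = √196 = 14; Φ(−20/14) = 7.7%.
- No Baseline, one earlier visit, r = 0.7×0.5 = 0.35: SD = √224.8 = 14.99; Φ(−1.334) = 9.1%.
- No Baseline, no earlier visit, r = 0: SD = √292 = 17.09; Φ(−1.170) = 12.1%.

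Simulation with 400,000 subjects gave 7.7%, 9.2% and 12.4%, and 7.5% to 7.7% with Baseline added. On the arm rate, 0.10 × (12.4 − 7.7) = 0.47 points (simulated 0.46). The slope of change on Baseline should be 0.5×16/12 − 1 = −0.333. With no earlier visit it becomes 0.9×0.667 − 1 = −0.400, as simulated. The residual variance of imputed values is 256 instead of 256×(1 − 0.25) = 192.

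**3. Simulated errors without Baseline, ρ from 0.3 to 0.7.**

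| Dropout | Earlier visit | Arm response rate (points) | Mean change in arm (SD 16) |
|---|---|---|---|
| MCAR | none | +0.09 to +0.66 | about 0 |
| MCAR | one | −0.04 to +0.23 | about 0 |
| Depends on Baseline | none | +0.96 to +3.04 | −0.5 to −1.1 |
| Depends on Baseline | one | +0.27 to +1.10 | −0.1 to −0.3 |

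With Baseline added, every arm rate is within 0.05 points of the truth. In an arm of 40, 3.04 points is 1.2 subjects and 1.10 points is 0.44. With the same dropout mechanism in both arms (ρ = 0.5, no earlier visit), the mean shifts are −0.76 and −0.77, so they nearly cancel in a contrast.

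**4. Two-arm ANCOVA (40 per arm, Baseline slope 0.6, true effect −6).** Early dropout linked to high Baseline, 15% against 5%, gave −5.2, an attenuation of 0.8/6 = 13%. At 20% against 5% it gave −4.8, or 1.2/6 = 20%. With 10% in both arms there was no bias, but the slope fell to 0.49 and the SD rose from 1.86 to 2.09 (a ratio of 1.12). With Week 4 data present the bias was negligible.

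**5. ACR50 from seven skewed components (active-like, true rate 39.6%, 10% missing).** Error in the arm rate, in points:

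| Post-Baseline visits observed | Without Baseline | With Baseline |
|---|---|---|
| none | −2.23 | −2.40 |
| Week 2 | −1.75 | −1.55 |
| Weeks 2, 4 | −1.51 | −1.45 |
| Weeks 2, 4, 8 | −1.42 | −1.34 |

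Adding Baseline moves the rate by at most 0.20 points and does not always help. Most of the error comes from the normal imputation model. The sign is also opposite to step 3.

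**6. Who is exposed.** All seven ACR components are scheduled at Weeks 2, 4 and 8 (Protocol 8.3.2 to 8.3.4). The Early Termination Visit collects them too (Protocol 8.5), and its values are mapped to a scheduled visit (SAP 3.5). But the FAS requires only a dose and a valid Baseline (SAP 3.6.4), so it can hold subjects with no post-Baseline value. mNAPSI is scheduled at Baseline (Protocol 8.2) and next at Week 12 (Protocol 8.3.5). SF-36 has only Week 4 in between.

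**The case against.** The best reply is that the SAP is silent on Baseline and does not exclude it. Its general description conditions on the observed data, and Baseline is observed. Sequential estimation brings in earlier visits, which carry Baseline information, and early termination values add more. The ACR50 logistic model contains only treatment, region and prior TNF exposure, all reflected in the imputation. The other continuous variables are summarised descriptively, so a direct mismatch with an analysis model is confined to supportive analysis 3.

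Most of this stands as a limit on size and reach. It does not remove the point. The covariate list is explicit and given twice, in a document meant to be sufficient for carrying out the analysis. A programmer who follows it leaves Baseline out, and one who adds Baseline departs from the specification. Earlier visits cannot help where there are none.

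A reader might infer that the imputed ACR50 responses are in fact distorted by the omission, and that adding Baseline would cure it. The documents give no basis for that. Baseline enters ACR50 only through its derivation, and the realistic simulation in step 5 shows almost the same error with and without it. A reader might also take the 13% to 20% attenuation as the expected size. It needs early, unbalanced, Baseline-linked dropout, and the documents give no dropout rate at all.

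**Conclusion.** The point holds as a weakness in a stated rule for which a better alternative is available. The firm part is structural: supportive analysis 3 adjusts for a variable that its imputation model does not contain. The size is conditional on the assumptions above. With earlier visits observed, the effect is small. It is larger for subjects with no post-Baseline value and for variables such as mNAPSI, and it biases a contrast only when Baseline-dependent dropout differs between arms. Some loss of precision can occur without bias.

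It would be wrong to conclude that the trial's formal results are at risk. The primary dose-response test and the pairwise ACR50 tests use NRI (SAP 8.1.2 and 8.1.3) and do not touch this model.

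**What to change.** In SAP 4.2.1, state that the Baseline value of the variable being imputed is a predictor in both the MCMC step and the monotone regression step. Apply this to the ACR components and to every other continuous variable that uses this MI.

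The cost is one extra predictor per model. Baseline is already collected, and no other analysis changes. This should not be presented as a repair of the ACR50 sensitivity analysis, where the gain is not established.

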4.2.2 Handling of missing data for AE

For analyses of AEs, a complete date must be established in order to correctly identify the AE as occurring during treatment or not. For purposes of imputing missing components of partially-reported start and stop dates for AEs, the algorithms listed below will be followed. Start and stop dates of AEs will be displayed as reported in the subject data listings (ie, no imputed values will be displayed in data listings).

Partial AE start dates will be imputed as follows:

Imputation of Partial Start Dates:

- If only the month and year are specified and the month and year of first dose is not the same as the month and year of the start date and the subject did not switch treatment during that month and year, then use the 1st of the month.
- If only the month and year are specified and the month and year of first dose is the same as the month and year of the start, then use the date of first dose.
- If only the month and year are specified and the subject did switch treatment during that month and year, then use the date of first switch treatment.
- If only the year is specified, and the year of first dose is not the same as the year of the start date and the subject did not switch treatment during that year, then use the 1st of January of the year of the start date.
- If only the year is specified, and the year of first dose is the same as the year of the start date, then use the date of first dose.
- If only the year is specified, and the year of first dose is the same as the year the subject did switch treatment, then use the date of first switch treatment.
- If only the year is specified, and the year of first dose is the same as the year of the start date and the same as the year the subject did switch treatment, then use the date of first dose.
- If the start date is completely unknown and the stop date is unknown or not prior to the date of first dose, then use the date of first dose.

If the date of first study medication or switch treatment is partial, then the above imputation approach will be applied:

- If only the day of first study medication or switch treatment administration is unknown, then this will be set to either the first of the month, or the day of first treatment allocation visit (excluding placebo run-in), whichever is later.
- If both the day and month of first study medication or switch treatment are unknown, then this date will be imputed to be the date of first treatment allocation visit.

- If first treatment allocation visit date is missing then the all activities events will be assumed to be treatment emergent.

Imputation of Partial Stop Dates:

- If only the month and year are specified, then use the last day of the month,
- If only the year is specified, then use December 31st of that year.
- If the stop date is completely unknown, do not impute the stop date.

In the event of ambiguity or incomplete data which makes it impossible to determine whether the AE was treatment emergent, the AE will be considered treatment emergent.

If the intensity of an AE is unknown, it is considered as severe.

If the relationship to study drug is missing, it is considered as related.

The imputation rule for missing seriousness differ between the interim and final analysis. For the interim analysis no imputations rule will be applied. For the final analysis the worst case approach will be applied. If the seriousness of an AE is missing for the final analysis, it is considered as serious.

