## **12 ASSESSMENT OF SAFETY**

### **12.1 Adverse events**

#### **12.1.1 Definition of adverse event**

An AE is any untoward medical occurrence in a patient or clinical investigation subject administered a pharmaceutical product that does not necessarily have a causal relationship with this treatment. An AE can therefore be any unfavorable and unintended sign (including an abnormal laboratory finding), symptom, or disease temporally associated with the use of a medicinal (investigational) product, whether or not related to the medicinal (investigational) product.

In order to ensure complete safety data collection, all AEs occurring during the study (ie, after the signing of the Informed Consent Form), including any pretreatment and posttreatment periods required by the protocol, must be reported in the eCRF even if no IMP was taken but specific study procedures were conducted. This includes all AEs not present prior to the initial visit and all AEs that recurred or worsened after the initial visit.

Signs or symptoms of the condition/disease for which the IMP is being studied should be recorded as AEs only if their nature changes considerably or their frequency or intensity increases in a clinically significant manner as compared to the clinical profile known to the Investigator from the subject's history or the Baseline Period.

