4.2.3 Handling of missing data for prior and concomitant medication

Any medications with incomplete start and end dates/times will be handled according to the following rules for classification as prior and concomitant. Such imputations will only be performed for these classifications and calculations; in the listings all data will be shown as recorded on the electronic case report form (eCRF).

Imputation of partial start dates:

- If only the month and year are specified and the month and year of first dose is not the same as the month and year of the start date and the subject did not switch treatment during that month and year, then use the 1st of the month.
- If only the month and year are specified and the month and year of first dose is the same as the month and year of the start, then use the date of first dose.
- If only the month and year are specified and the subject did switch treatment during that month and year, then use the date of first switch treatment.
- If only the year is specified, and the year of first dose is not the same as the year of the start date and the subject did not switch treatment during that year, then use the 1st of January of the year of the start date.
- If only the year is specified, and the year of first dose is the same as the year of the start date, then use the date of first dose.
- If only the year is specified, and the year of first dose is the same as the year the subject did switch treatment, then use the date of first switch treatment.
- If only the year is specified, and the year of first dose is the same as the year of the start date and the same as the year the subject did switch treatment, then use the date of first dose.

- If only the year is specified and the end date is before date of first dose, then set the start date to the 1st of January of the year of the start date.
- If only the year and day are specified and month is missing, then only the year will be considered and the month and day will be imputed with the rules above
- If the start date is completely unknown and the stop date is unknown or not prior to the date of first dose, then use the date of first dose.
- If the start date is completely unknown and the stop date is prior to the date of first dose, then set the start date to the 1st of January of the year of the end date.

If the date of first study medication or switch treatment is partial, then the above imputation approach will be applied:

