6.4 Prior and concomitant medications

Prior medications include any medications that started and ended prior to the start date of study medication. Concomitant medications are medications taken at least one day in common with the study medication dosing period. For bimekizumab, the dosing period is typically from the date of first dose up to (but not including) one dosing interval post last dose. Thus, a concomitant medication is any medication whose start date is on or after the date of first study medication and prior to the date of last study medication administration + 28 days (1 dosing interval), or whose stop date is either missing, or on or after the date of first study medication administration.

In the case of missing data, the classification of medications as prior or concomitant will be performed as described in [Section 4.2.3](#).

The number and percentage of subjects taking prior medications will be summarized by treatment group, overall and by anatomical therapeutic chemical (ATC) class, presenting Anatomical Main Group (ATC Level 1), Pharmacological Subgroup (ATC level 3), and PT.

The number and percentage of subjects taking concomitant medications will be summarized similarly. Tables for prior and concomitant medications will be presented for SS and FAS.

Prior and concomitant medications will be listed by treatment and subject for RS.

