10.2 Adverse events

An AE is any untoward medical occurrence in a patient or clinical investigation subject administered a pharmaceutical product that does not necessarily have a causal relationship with this treatment. An AE can therefore be any unfavorable and unintended sign (including an abnormal laboratory finding), symptom, or disease temporally associated with the use of a medicinal (investigational) product, whether or not related to the medicinal (investigational) product.

AEs (including serious AEs) are characterized as either non-treatment or treatment emergent according to the following criteria:

- Non-treatment emergent are the events with onset date and time prior to the very first administration of study medication (bimekizumab or placebo) or after a 140-day period after the final drug administration.
- Treatment-emergent AEs (TEAE) are those with onset date at or after the very first administration of study medication. The events that emerge within 140 days after the final drug administration, will also be considered as treatment emergent (eg, in the case of premature discontinuation or during the Safety Follow-up [SFU] period).

All AEs occurring during the study (i.e., after signature of the informed consent document) will be recorded in the eCRF. For each AE the following information will be recorded in the eCRF: AE term (verbatim term), date of onset, whether or not the AE was classified as a SAE, as an AE of special interest, intensity, relationship to study medication, action taken with study medication, other action taken, outcome, date of outcome, and whether the AE led to study drug discontinuation or to study discontinuation.

ADRs are defined as a response to a drug which is noxious and unintended and which occurs at doses normally used in man for prophylaxis, diagnosis, or therapy of disease or for modification of physiological function. Any AE that is considered "Related" to study treatment will be classed as an ADR.

If an AE occurs on the same day as the treatment switch (Visit 7, Week 12) then the AE will be allocated to the Double-Blind treatment. An exception from this general rule is made for ADRs, and AE of hypersensitivity reactions and anaphylactic reactions. If those AEs occur on the same days as the treatment switch, the AEs will be allocated to the Dose-Blind treatment.

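### SAP start-date imputation ignores a known earlier stop date, so some adverse events that ended before first dose are counted as treatment-emergent and some short medication courses as concomitant

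*SAP*

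**What the plan says.** **Adverse events.** SAP 4.2.2 gives the purpose of the imputation: "a complete date must be established in order to correctly identify the AE as occurring during treatment or not". For a start recorded by month and year alone, it says that if "the month and year of first dose is the same as the month and year of the start, then use the date of first dose". A year-only start in the first-dose year is treated the same way, and a month-year start in the month of the treatment switch is set to the switch date. The only start rule that consults the stop date is the one for a wholly missing start: "If the start date is completely unknown and the stop date is unknown or not prior to the date of first dose", use the first dose. Section 4.2.2 has no rule for a wholly missing start with a stop before first dose. Its closing default begins "In the event of ambiguity or incomplete data which makes it impossible to determine whether the AE was treatment emergent" and then treats the event as emergent.

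**Classification.** SAP 10.2 reads: "Treatment-emergent AEs (TEAE) are those with onset date at or after the very first administration of study medication". Duration (SAP 10.2.1, equation 40) is outcome date minus onset date plus 1, using the imputed onset.

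**Medications.** SAP 4.2.3 repeats the month-year rule unchanged but protects the other two cases. One guard reads "If only the year is specified and the end date is before date of first dose, then set the start date" to 1 January of the start year. The other sets a wholly unknown start with a stop before first dose to 1 January of the stop year. SAP 6.4 then states: "Prior medications include any medications that started and ended prior to the start date of study medication". A medication is concomitant if it starts on or after first dose (and before last dose plus 28 days), or if its stop is missing or on or after first dose.

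**The concern.** A stop date before first dose settles that the event or the drug course was over before treatment began. The imputation overrides that recorded fact and produces a start later than the stop. This works against the section's stated purpose, and the closing default does not cover it, because that default is reserved for events whose status cannot be determined.

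Pre-treatment events are in the database: Protocol 12.1.1 requires reporting of "all AEs occurring during the study (ie, after the signing of the Informed Consent Form", and Screening lasts 14 to 28 days. At stake are TEAE incidence, the exposure-adjusted rates built on it, AE durations and, through the switch-month rule, the treatment to which a related event is attributed. For medications, it is the split between the prior and concomitant tables. The guards in 4.2.3 show that the sponsor already accepts the logic but has not applied it throughout.

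**Working it through.** The plan states no figure for this rule, so the check applies the rules as written. The dates are illustrative.

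**1. AE, month-year start.** Recorded start Jan 2017; stop 10 Jan 2017; first dose 15 Jan 2017.
- Start month equals first-dose month, so onset = 15 Jan.
- Onset is at or after first dose, so TEAE = yes.
- Duration = 10 − 15 + 1 = −4 days.

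A second case, with first dose 20 Mar and stop 10 Mar, gives 10 − 20 + 1 = −9 days.

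**2. Range.** For this pattern, duration = stop − first dose + 1. A stop on the day before dosing gives −1 + 1 = 0. A stop 28 days before dosing, the limit of the longest Screening Period, gives −28 + 1 = −27. The duration is therefore always zero or negative.

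**3. AE, year-only start.** The first-dose date is again used without a stop-date check, so any such event in the first-dose year that is known to have stopped before dosing has the same outcome.

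**4. Switch month.** Let S be the switch date (Week 12) and D a known stop in the same month with D < S. Onset is set to S and duration is D − S + 1 ≤ 0. Under SAP 10.2 an AE dated on the switch day normally stays with Double-Blind treatment, but related events (ADRs) and hypersensitivity or anaphylactic reactions go to Dose-Blind treatment. A related event that began and ended on placebo would therefore be counted under bimekizumab. The complete-period tables, which show only events under bimekizumab and carry the exposure-adjusted rates, would include it.

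**5. Medications.** First dose 20 Mar 2017; stop 10 Mar 2017.

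| Recorded start | Imputed start | Prior? | Concomitant? |
|---|---|---|---|
| Mar 2017 | 20 Mar | No (start not before first dose) | Yes (start on or after first dose) |
| Feb 2017 | 1 Feb | Yes | No |

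The two concomitant conditions are joined by *or*, so the early stop does not undo the first. The error is confined to starts in the first-dose month; year-only and unknown starts are guarded.

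**6. Which drugs can be affected.** The start must fall in the first-dose month, so the stop can precede dosing by at most 31 − 1 = 30 days. Protocol Tables 7-1 and 7-2 require 12 weeks (84 days) for most DMARDs, 3 months for most TNF inhibitors and for systemic retinoids, and 6 months for leflunomide without cholestyramine washout. None of these fits within 30 days if the washout is respected. A 28-day washout fits only when the drug was both begun and stopped in the first days of a long month. What remains is short courses and short-washout agents, such as the 14-day topicals, begun in that month.

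**7. Calendar reach.** Assume first-dose dates spread evenly over a year. The share of pre-dose days that falls in the first-dose calendar month is then about 75% for a 14-day Screening, 64% for 21 days and 52% for 28 days. These are shares of days, not counts of records.

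**8. After correction.** In case 1, a 14- to 28-day Screening puts consent between 18 Dec and 1 Jan. The later of 1 Jan and consent is 1 Jan, so the event is not treatment-emergent and lasts at most 10 − 1 + 1 = 10 days. In case 5, the March drug starts on 1 Mar and is prior.

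**The case against.** The strongest reply is that this is a small drafting gap with a conservative direction. Over-counting TEAEs matches the SAP's other defaults (unknown intensity taken as severe, missing relationship as related). The first-dose rule is the same in every arm, so no differential bias is shown. Listings show dates as reported, so affected records can be found. The governing definitions also point the right way: SAP 3.2.1 gives a negative relative onset day to an event that started and stopped before first dose, and SAP 6.4 describes concomitant use as sharing at least one day with the dosing period.

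Much of that stands as a limit on importance, but it does not repair the rule. Summary tables use the imputed date, and the operational definitions in 10.2 and 6.4 act on it. The switch-month rule is not neutral across treatments, because its misattribution affects only subjects whose treatment changes at Week 12. A conservative default is for undetermined cases, and these are determined.

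Two further cautions are right. The documents give no frequency for partial dates; the AE pattern needs a missing onset day together with a stop known to precede dosing, and the count could be zero. A simple remedy of 1 January or the first of the month could also place an AE before consent. With consent on 20 Oct, stop on 1 Nov and first dose on 10 Nov 2017, a year-only start set to 1 January gives 305 days, whereas the longest possible on-study duration is 13 days (20 Oct to 1 Nov inclusive).

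**Conclusion.** The rule is wrong as written for a defined set of records. These are AEs with a month-year start in the first-dose month or a year-only start in the first-dose year, and medications with a month-year start in the first-dose month, where in each case the stop is known to precede first dose. Every such record is misclassified, and every such AE has a zero or negative duration. The switch-month rule produces the same impossible date order and reassigns related events to the later treatment.

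The number of records is not given and may be small. Efficacy analyses, including ACR50 at Week 12, are unaffected.

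A reader might infer that therapies washed out for the study generally disappear from the prior-medication table. The documents do not support that: drugs started in an earlier month are classified correctly, year-only and unknown starts are guarded, and agents with washouts of 12 weeks or longer cannot be affected if the washout is respected. Nor do the documents support a claim that TEAE rates are materially inflated or that arms are differentially biased by the first-dose rule. The case for changing it is that the error is certain where the pattern occurs and the correction is simple.

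**What to change.** Add to SAP 4.2.2 and 4.2.3:

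- An imputed start date must never be later than the known (or imputed) stop date.
- A record whose stop date is before first dose is classed as non-treatment-emergent (AE) or prior (medication), whatever part of the start date is missing.
- An AE whose stop date is before the treatment switch stays with the pre-switch treatment.
- In these cases, impute an AE start to the later of (a) the first day of the stated month, or 1 January of the stated year, and (b) the informed consent date. For a medication with a month-year start, use the first of the stated month.

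The consent bound keeps imputed AE starts within the reporting period and avoids inflated durations. The cost is one short rule in each of two SAP sections and the matching programming change. No new data are needed and no efficacy analysis changes. A check of the AE and medication data for imputed starts later than stops would show how many records are affected before final tables are produced.
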